### ***11.2.3 Minimal Evaluation Visit***

- Vital signs including blood pressure and pulse rate.
- Retrieval of previous subject DRC.
- Recording of seizures.
- Recording of workdays and schooldays lost and days subject received help from a caregiver (paid or not) at home during the first 2 years.
- Hospital stay during the first 2 years.
- Healthcare provider consultation not foreseen by protocol during the first 2 years.
- Recording of Adverse Events.
- Assessment of suicidality (C-SSRS).
- Medical procedures.
- Concomitant medications (AED and Non-AED) documentation.
- Drug return/accountability including study medication intake and compliance check.
- Dispensation of new DRC.
- Dispensation of study medication.
- Appointment for the next visit according to the schedule described in Section 5.2.

### ***11.2.4 Yearly Evaluation Visit (replaces the first FEV of each year)***

- Vital signs including blood pressure and pulse rate.
- Body weight and height (only for those subjects still potentially growing).
- Physical and neurological examination.
- ECG.
- Retrieval of previous subject DRC.
- Recording of seizures.

- Laboratory assessment including safety (hematology, blood chemistry, and urinalysis), urine pregnancy test (if applicable).
- Recording of Adverse Events.
- Assessment of suicidality (C-SSRS).
- Medical procedures.
- Concomitant medications (AED and Non-AED) documentation.
- Drug return/accountability including study medication intake and compliance check.
- Dispensation of new DRC.
- Dispensation of study medication.
- Appointment for the next visit according to the schedule described in Section 5.2.

The following assessments will be performed during the first 2 years which includes the YEV in Year 3.

- QOLIE-31-P questionnaire (except if subject mentally impaired and except for all subjects coming from N01193). The questionnaire should be filled in at the beginning of the Visit.
- HADS questionnaire (except if subject mentally impaired and except for all subjects coming from N01193). The questionnaire should be filled in at the beginning of the Visit, after the QOLIE-31-P.
- Healthcare provider consultation not foreseen by protocol
- Recording of workdays and school days lost and days subject received help from a caregiver (paid or not) at home.
- Hospital stay.
- EQ-5D questionnaire (except if subject mentally impaired and except for all subjects coming from N01193).
- Socio-professional data.

#### ***11.2.5 Early Discontinuation Visit***

- Vital signs including blood pressure and pulse rate.
- Body weight.
- Physical and neurological examination.
- ECG
- Retrieval of previous subject DRC.
- Recording of seizures.
- Laboratory assessment including safety (hematology, blood chemistry, and urinalysis), urine pregnancy test (if applicable).
- Recording of Adverse Events.
- Assessment of suicidality (C-SSRS).
- Medical procedures.
- Concomitant medications (AED and Non-AED) documentation.

- Drug return/accountability including study medication intake and compliance check.
- Dispensation of new DRC.
- Dispensation of study medication with down-titration dosing schedule.
- Appointment for the next visit according to the schedule described in Section 5.2.

Down-titration may not be applicable to subjects who may transition to another BRV study or may be initiated in a managed access program or similar type of program.

The following assessments will be performed only if the EDV occurs within the first 2 years.

- QOLIE-31-P questionnaire (except if subject mentally impaired and except for all subjects coming from N01193). The questionnaire should be filled in at the beginning of the Visit.
- HADS questionnaire (except if subject mentally impaired and except for all subjects coming from N01193). The questionnaire should be filled in at the beginning of the Visit, after the QOLIE-31-P.
- Healthcare provider consultation not foreseen by protocol
- Recording of workdays and schooldays lost and days subject received help from a caregiver (paid or not) at home.
- Hospital stay.
- EQ-5D questionnaire (except if subject mentally impaired and except for all subjects coming from N01193).
- Socio-professional data.

#### **11.2.6 Down-Titration Phone Call**

- Recording of Adverse Events.
- Reminder of appointment for the next visit according to the schedule described in Section 5.2.

#### **11.2.7 Final Visit (FV following a Study Drug Free Period after an EDV or FV initiated upon Sponsor request at the end of the program)**

- Vital signs including blood pressure and pulse.
- Body weight and height (only for those subjects still potentially growing).
- Physical and neurological examination.
- ECG (except after an EDV when EDV ECG results were normal).
- Retrieval of previous subject DRC.
- Recording of seizures.
- Recording of workdays and school days lost and days subject received help from a caregiver (paid or not) at home during the first 2 years.
- Hospital stay during the first 2 years.

- Healthcare provider consultation not foreseen by protocol during the first 2 years.
- Laboratory assessment including safety (hematology, blood chemistry, and urinalysis), urine pregnancy test (if applicable).
- Recording of Adverse Events.
- Assessment of suicidality (C-SSRS).
- Medical procedures.
- Concomitant medications (AED and Non-AED) documentation.
- Drug return/accountability including study medication intake and compliance check.
- Completion of end of study status.
- Retrieval of “Clinical Study Subject Card”.

### **11.2.8 Additional Visit**

At any time, the subject may have an additional study visit/phone call if the Investigator or the subject deems it necessary. All information, including reason for visit/phone call, any information on AEs, etc., should be collected in the source documents and recorded in the appropriate section of the CRF. Study medication can be dispensed if required.

### **11.3 Handling of Biological Samples**

The safety samples (hematology, biochemistry, urinalysis, pregnancy test) will be routinely assayed and the results sent by fax and letter to the Investigators as specified in Section 11.1.14.

### **11.4 Other Supplies**

Not applicable.

## **12 ADVERSE EVENTS AND SERIOUS ADVERSE EVENTS**

### **12.1 Adverse Events**

#### **12.1.1 Definition of Adverse Event (AE)**

An adverse event is any untoward medical occurrence in a patient or clinical investigation subject administered a pharmaceutical product which does not necessarily have a causal relationship with this treatment. An adverse event can therefore be any unfavorable and unintended sign (including an abnormal laboratory finding), symptom, or disease temporally associated with the use of a medicinal (investigational) product, whether or not related to the medicinal (investigational) product.

In order to ensure complete safety data collection, all AEs or undesirable experiences occurring during the study (i.e., after signature of the Informed Consent), including any pre-

and post-Treatment Periods required by the protocol, must be reported even if no investigational product was taken but specific study procedures were conducted. These include all AEs not present prior to the initial visit and all AEs which recurred or worsened after the initial visit.

Signs or symptoms of the condition/disease for which the investigational product is being studied should be recorded as AEs only if their nature changes considerably or their frequency or intensity increases in a clinically significant manner as compared to the clinical profile known to the Investigator from the subject's history or the baseline period.

### **12.1.2 Procedures for Reporting and Recording Adverse Events**

The study participant will be given the opportunity to report Adverse Events spontaneously. A general prompt will also be given to detect adverse events, e.g.,

“Did you notice anything unusual about your health (since your last visit)?”

In addition, the Investigator should review any self-assessment procedures (e.g., diary cards) employed in the study.

### **12.1.3 Description of AEs**

The following guidelines and definitions should be used by the Investigator for the description of an AE when reporting information:

Nature of the AE:	Preferably an overall diagnosis or syndrome, rather than individual symptoms or signs. The Investigator must report adverse events using standard medical terminology. The CRF and source documents should be consistent. Any discrepancies between the subject's own words on his/her own records (e.g., diary card) and the corresponding medical terminology should be clarified in the source documentation.
Date of onset:	Date the AE started.
Pattern:	
Intermittent	The AE recurs with the same intensity at various intervals throughout the entire time period specified. There were intervals within the specified time period when the AE was not present.
Continuous	The AE is present at the same intensity for the entire time period specified. There was no time at which the event abated or was not present during the time period specified.

Intensity:

- |          |  |
|----------|--|
| Mild     | The subject is aware of the sign or symptom (syndrome), but it does not interfere with his/her usual activities and/or it is of no clinical consequence. |
| Moderate | The AE interferes with the usual activities of the subject or it is of some clinical consequence.  |
| Severe   | The subject is unable to work normally or to carry out his/her usual activities, or the AE is of definite clinical consequence.                          |

Action taken with investigational product:

- |                  |  |
|------------------|--|
| Not applicable   | For AEs occurring during the study drug free period.                               |
| No change        | Investigational product dosing remained the same in spite of the AE being present. |
| Dosage increased | Investigational product dose was increased because of this AE.                     |
| Dosage decreased | Investigational product dose was decreased because of this AE.                     |

Temporarily discontinued  
Investigational product was temporarily discontinued because of this AE, either because the subject chose to discontinue the study drug or the physician felt it was in the subject's best interest to temporarily discontinue the investigational product.

Permanently discontinued  
Investigational product was permanently discontinued because of this AE, either because the subject chose to discontinue the study drug or the physician felt it was in the subject's best interest to discontinue the investigational product.

Other actions taken:  
If action taken other than study drug, the appropriate sections should be completed: Medications, Medical procedures.

Outcome:

- |                       |  |
|-----------------------|--|
| Resolved              | The AE is no longer present at any intensity - completely abated.  |
| Resolved with sequela | The AE is resolved but residual effects are still present.   |
| Ongoing               | The AE is still present at the last contact with the subject. If the AE is marked "ongoing", the outcome date should be blank. |
| Worsened              | The AE is still present but at a heightened intensity. The rule of repetition of AE reporting should be applied.               |

This document cannot be used to support any marketing, distribution application or any extensions or variations thereof.

Fatal	This AE caused or directly contributed to the subject's death.
Date of outcome:	Date the AE abated. If the AE consists of several signs and symptoms (syndromes), the sign or symptom with the longest duration determines the duration of the AE. If the AE is marked "ongoing", the outcome date should be blank.
Relationship to study drug: None	Only applicable when no investigational product was taken or when the subject is taking single-blind placebo, or when the AE can be ascribed with reasonable certainty to another cause (e.g., a gun shot wound).
Unlikely	There are good reasons to think that there is no relationship (e.g., the AE is a known adverse drug reaction of a concomitant medication).
Possible	Equally valid arguments can be considered for or against an implication of the investigational product. For example, the AE: 

• follows a reasonable temporal sequence from the administration of the investigational product.

• follows a known or expected response pattern to the investigational product.

• but could readily have been produced by a number of other factors.

Probable	The relationship is likely. For example, the AE: 

• follows a reasonable temporal sequence from administration of the investigational product.

• follows a known or expected response pattern to the investigational product.

• is confirmed by improvement on stopping or reducing the dosage of the investigational product.

• could not be reasonably explained by the known characteristics of the subject's clinical state.

This document cannot be used to support any marketing, promotional, or other applications and extensions or variations thereof.

Highly probable

There is a strong relationship. For example, the AE:

- follows a reasonable temporal sequence from administration of the investigational product.
- follows a known or expected response pattern to the investigational product.
- is confirmed by improvement on stopping or reducing the dosage of the investigational product, and reappearance on repeated exposure (re-challenge).

#### ***12.1.4 Follow-up on Adverse Events***

If an AE is still ongoing at the time the CRF is collected, a follow-up report should be provided at a later date. If no follow-up report is provided, the Investigator must provide a justification.

The Sponsor may request that the Investigator perform or arrange for the conduct of supplementary measurements and/or evaluations (e.g., re-challenge procedure).

A serious AE or an AE leading to premature discontinuation from the study must always be followed up until it has resolved or the Investigator no longer feels it is clinically significant.

#### ***12.1.5 Rule for Repetition of an AE***

An unexpected increase in the intensity of an AE should lead to the repetition of the AE reporting with:

- the outcome date of the first AE that is not related to the natural course of the disease being the same as the start date of the repeated AE.
- the Investigator's original description of the AE being the same for the first and repeated AE.

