#### **11.1.15 Adverse Events (AEs)**

At the Entry Visit, the Investigator will record any adverse event that was still ongoing at the end of the previous study. From the entry Visit onwards, adverse events will be assessed at each visit and recorded in the CRF and in the source documents. The study participant will be given the opportunity to report AEs spontaneously. A general prompt will also be given to detect AEs, e.g., "Did you notice anything unusual about your health (since your last visit)?" In addition, the Investigator should review any self-assessment procedures (e.g. daily record cards) used in the study.

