11.2 Adverse events

11.2.1 Definition of treatment-emergent AE

AEs will be classified as either pre-study or treatment-emergent. Pre-study AEs are defined as AEs which had onset prior to the date of the first dose of BRV. TEAEs are defined as AEs that had onset on or after the day of first BRV dose. AEs with an incomplete onset date will be classified as TEAEs if the month and year of onset (when only the month and year are specified) is the same as the month and year of the first BRV dose or the year of onset (when only year is specified) is the same as the year of first BRV dose.

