11.2.2 General summaries of TEAEs

Pre-treatment AEs will be provided in a subject data listing; no summaries of pre-treatment AEs are planned.

An overall summary of AEs will provide the overall number of TEAEs and the numbers and percentages of subjects with at least 1 TEAE, with a TEAE that led to permanent discontinuation of study drug, with a drug-related TEAE, with a severe TEAE, with a treatment-emergent SAE, and with a drug-related treatment-emergent SAE. The number and percentage of subjects who died will also be summarized. This summary will be provided for all subjects in the Safety Analysis Set and also by subgroup for geographic region and seizure type.

The following summaries of TEAEs will be provided by MedDRA SOC and PT. All summaries are for the combined Evaluation, Down-Titration, and Post-Treatment Periods unless otherwise indicated.

Overall Incidence Summaries

- Incidence of TEAEs
- Incidence of TEAEs by 3-month time interval
- Incidence of TEAEs by study period (Evaluation, Down-Titration, Post-Treatment)
- Incidence of TEAEs for TEAEs occurring in at least 5% of subjects
- Incidence of TEAEs by 3-month time intervals for TEAEs occurring in at least 5% of subjects overall
- Incidence of non-serious TEAEs occurring in at least 5% of subjects

The incidence of TEAEs occurring in at least 5% of subjects will be summarized overall as noted above and also by subgroup for geographic region, seizure type, and randomized treatment from the previous double-blind study.

A subject is included in a 3-month interval if the subject was receiving BRV at any time during that interval based on their duration of exposure to BRV (eg, a subject with exposure for 91 days is included in the time interval for Months 1-3 and Months 4-6). Summaries of AEs by 3-month intervals will include all subjects who are classified into each time interval

as defined above. TEAEs which had onset prior to or on the date of the last dose of BRV are included in summaries by 3-month time intervals.

Maximum Intensity and Causality

- Incidence of TEAEs by maximum intensity
- Incidence of drug-related TEAEs

Serious Adverse Events

- Incidence of treatment-emergent SAEs

Discontinuations due to TEAE

- Incidence of TEAEs leading to permanent discontinuation of study drug

TEAEs of interest

AEs of interest will be identified based on MedDRA search criteria, which are documented outside of the SAP. The following summaries will be provided for AEs of interest:

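### The onset-only TEAE definition leaves carried-over AEs that turn serious or end treatment without a rise in intensity out of the TEAE and SAE tables; for rises in intensity the recording rules conflict

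*Protocol*

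**What the plan says.** **Recording.** Protocol 11.1.15 brings AEs from the previous study into the database: "At the Entry Visit, the Investigator will record any adverse event that was still ongoing at the end of the previous study". Protocol 12.1.1 puts "all AEs which recurred or worsened after the initial visit" within the reporting duty. Protocol 12.1.5 says when a second record is opened: "An unexpected increase in the intensity of an AE should lead to the repetition of the AE reporting". The second record starts on the outcome date of the first. Protocol 12.1.3 defines the outcome code Worsened without the qualifier 'unexpected': "The AE is still present but at a heightened intensity. The rule of repetition of AE reporting should be applied".

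**Classification.** SAP 11.2.1 uses onset date alone: "Pre-study AEs are defined as AEs which had onset prior to the date of the first dose of BRV". Onset on or after the day of that dose makes the event a TEAE. SAP 3.2.1 fixes the reference as the first dose in N01199, not in the previous study. Neither section has a clause for worsening, for becoming serious or for leading to discontinuation.

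**Reporting.** SAP 11.2.2 sends AEs that precede treatment to a listing, and "no summaries of pre-treatment AEs are planned". The tables for SAEs and for discontinuation are limited to treatment-emergent events. SAP 2.2.1.1 names three primary safety variables: occurrence of a TEAE, withdrawal due to an AE, and occurrence of an SAE. The last two carry no treatment-emergent limit.

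**The concern.** An onset-only definition is workable if every relevant change in an old event creates a new dated record. Here the only mechanism for that is the repetition rule, and it responds to intensity alone. Seriousness and discontinuation are separate attributes of an AE, and no rule attaches a new date to either.

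N01199 is a rollover study whose primary objective is long-term safety, and its subjects include some who received placebo in the previous study (SAP 4.8). An event that began there and became serious after BRV was started or increased is one that a safety table should show. As written, it can be absent from the SAE table, and the omission can only lower the reported incidence.

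Where intensity does rise, the difference between 12.1.5 and 12.1.3 means that the TEAE count partly reflects which section a site followed.

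**Working it through.** Neither document gives a figure on this point that could be reproduced, and no sample size or power calculation is involved. The check traces an AE that is ongoing at the Entry Visit through the rules.

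**Case A: intensity rises on N01199 and the rise is judged unexpected.** Protocol 12.1.5 and 12.1.3 both call for repetition. The new record starts after the first N01199 dose, so SAP 11.2.1 makes it a TEAE. It is counted correctly.

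**Case B: intensity rises and the rise is not judged unexpected.** Under 12.1.5 read alone there is no second record, so the event keeps its old onset and is only listed. Under 12.1.3 the outcome is Worsened, the record is repeated, and the event is a TEAE. Protocol 12.1.1 requires the worsening to be reported but does not say that it receives a new start date, so it does not settle the matter.

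**Case C: the event becomes serious with no rise in intensity.** Protocol 12.1.5 and 12.1.3 are not triggered, and no other section opens a record or resets onset. SAP 11.2.1 classes the event as pre-study. It is missing from the TEAE and treatment-emergent SAE tables.

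**Case D: the event leads to permanent discontinuation with no rise in intensity.** The reasoning is the same as in case C. The event is missing from the table of TEAEs leading to discontinuation by system organ class and preferred term. The subject is still counted under the adverse event reason in the disposition summary (SAP 5.1).

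**Size per subject.** The only usable input is the 668 enrolled subjects (SAP 2.4); the size of the Safety Analysis Set is not stated. If k subjects are missed and have no other event that qualifies them for the same row, the incidence is understated by 100 × k / 668 percentage points:

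- k = 1: 100 × 1 / 668 = 0.15
- k = 5: 100 × 5 / 668 = 0.75
- k = 10: 100 × 10 / 668 = 1.50
- k = 20: 100 × 20 / 668 = 2.99

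The values of k are illustrations. The documents do not say how many AEs were carried over or how many later changed.

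**The case against.** The strongest reply is that the protocol does provide for worsening. Protocol 12.1.3 sends every heightened intensity to the repetition rule and 12.1.1 requires worsened AEs to be reported, so the onset-only definition then works as intended. This stands for cases A and B to the extent that sites follow 12.1.3. A reader might infer that expected worsening of a carried-over AE is always excluded from the tables. The documents do not support that: they conflict, and the conflict is not resolved in favour of 12.1.5.

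A reader might also take 'unexpected' to mean not already known for BRV, so that worse somnolence after a dose increase would not be re-recorded. No section says so. Expectedness against the Investigator's Brochure appears in Protocol 12.2.2 and concerns SAEs. The first bullet of 12.1.5 refers, awkwardly, to the natural course of the disease, which points to a different benchmark.

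On case C, an AE that becomes serious will often also rise in intensity, because the severe grade in 12.1.3 includes definite clinical consequence. That narrows the gap, chiefly to AEs already graded severe at entry and to events whose grade the site leaves unchanged. It does not close it, since the seriousness criteria in 12.2.1 are not tied to intensity.

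Finally, the events are not hidden. They stay in the listings, SAEs must reach the sponsor within 24 hours (Protocol 12.2.2), deaths are summarised without a stated onset condition (SAP 11.2.2), and disposition counts withdrawals for AEs. All of this stands. The defect is in the summary tables, not in safety surveillance.

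**Conclusion.** The point holds in two parts. First, a carried-over AE that becomes serious or leads to discontinuation with no rise in intensity is classed as pre-study and left out of the treatment-emergent tables. This follows directly from the text. It matters most for SAEs, because the SAP's only SAE incidence table is narrower than the primary safety variable it serves. Second, for a carried-over AE whose intensity rises, Protocol 12.1.5 and 12.1.3 give different triggers, so identical events may be counted differently between sites. That is an inconsistency, not a settled exclusion.

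The total effect cannot be computed. One could multiply an assumed share of subjects with carried-over AEs by an assumed share that change, but neither share has any basis in the documents. A subject with another TEAE is already counted in the overall TEAE row. What can be said is that each missed subject with no other qualifying event is about 0.15 points, taking 668 as the denominator, and that the direction is towards lower reported incidence. For infrequent SAEs a few subjects could be visible. The correction is cheap and bears on primary safety variables, so it should be made.

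**What to change.** **SAP 11.2.1.** Add a clause such as: an AE with onset before the first N01199 dose of BRV is also treatment-emergent if, on or after the day of that dose, it increases in intensity, becomes serious, or leads to permanent discontinuation of BRV; for period and 3-month summaries it is dated at that change. Count it as an SAE only where it became serious on or after that dose, and do not count the same change twice where a repeated record already exists. Cases can be identified from repeated records, the Worsened outcome code, the action taken with study drug, and SAE reports. A footnote giving the number of events that enter through the clause would keep the tables transparent.

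**Protocol 12.1.5.** Reconcile it with 12.1.3 and 12.1.1 so that sites have one trigger for the remaining follow-up. Enrolment is complete (SAP 2.4), so this cannot recover past rises in intensity that were never recorded. The SAP clause is therefore the more useful change.

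**Cost.** One SAP clause, a small matching task between carried-over AEs and SAE reports with some date queries, and one protocol wording change. TEAE and SAE percentages may become slightly less favourable.
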